#### **9.4 Recording and reporting of SAEs, SADEs and USADEs**

This study uses CE marked devices and is not regulated by the Medicines and Healthcare products Regulatory Agency (MHRA). All SAE/SADE/UADEs need to be reported to the sponsor R&D **within one working day** of the investigator team becoming aware of them. The Chief Investigator will assess the event for expectedness using the current study protocol, see section 9.5 Known (expected) complications associated with Toric IOL surgery.

Reports of related and unexpected SAEs/ SADE's should be submitted by the Sponsor to ethics within 15 days of the Chief Investigator or Principal becoming aware of the event, using the SAE report form for non-CTIMPs published on the HRA website.

All reporting to R&D should be by e-mail the Research Governance Manager (RGM) or their Deputy giving as much information about the incident as possible.

The RGM will undertake an initial review of the information. Events will be followed up until resolution, any appropriate further information will be sent by the research team in a timely manner. Any events continuing at the end of the study will be followed up by the participants GP and/ or the routine clinical care team until discharge. This will apply to participants who withdraw from the study.

Reporting to the Manufacturer will be done in liaison with the Chief Investigator.

The Manufacturer has a legal obligation to report all events that need to be reported to the Nominated Competent Authority immediately (without any unjustifiable delay) if a link is established between the event and the device, but no more than:

Vision and balance changes after bilateral implantation of Toric IOLs  
IRAS ID: 286913

- 2 days following the awareness of the event for Serious Public Health Threat.
- 10 days following awareness of the event for Death or unanticipated serious deterioration in health.
- 30 days following the awareness of the event for all other event meeting the SAE criteria.

In the event of an accident, incident or near miss relating to cataract surgery or clinical care or happens at the Derriford Hospital, in addition to previous reporting requirements, the recording and reporting should follow the Incident Management Policy of the University Hospitals of Plymouth NHS Trust. The PI or need to report *via* UHP Datix and notify the CI and Sponsor.

In addition, all accidents, incidents, near misses during study visit at PAHC building of UoP must be reported following the Universities internal procedures. The CI will assess the seriousness of the event for reporting to the Health and Safety Department according to [the Health and Safety Policy](#) of the University and notify the sponsor and PI.

### **9.5 Known (expected) complications associated with Toric IOL surgery**

#### Intraoperative risks

- Anterior segment bleeding
- Posterior capsular rupture
- Zonular dehiscence
- Incomplete continuous curvilinear capsularhexis
- Severe iris/corneal Trauma
- Anterior vitrectomy

#### Post-operative complications:

- endophthalmitis (inflammation of the internal eye tissues, most commonly caused by an infection) and bleeding.
- irregular astigmatism
- dry eye
- keratectasia (progressive myopia, irregular astigmatism, ghosting, fluctuating vision and problems with scotopic vision. The progression leads to severe loss of corrected visual acuity)
- Patient reported subjective complaints of halos, glare, and ghost images.
- Wound leak
- Flat anterior chamber
- Hyphema
- Vitreous in anterior chamber
- Vitreous in wound

Vision and balance changes after bilateral implantation of Toric IOLs  
IRAS ID: 286913

- Raised IOP
- Pupillary block
- Anterior synechiae
- Posterior synechiae
- Deposits on IOL
- Fibrin in Pupil
- Nuclear remnants
- Cortical Remnants
- Retinal detachment
- Cystoid macular oedema
- Anterior capsular Opacification
- Posterior capsular opacification
- Intraocular lens tilt and decentration
- Cells/flare in the anterior chamber

Toric IOLs have a few other potential complications. Astigmatism may be overcorrected or under-corrected.

As mentioned previously, the Toric IOL may rotate off-axis. There will be some partial effect if it rotates off-axis. For example, the correction effect of the Toric IOLs is reduced by 10% for every 3° rotation off-axis. For the lens to lose its full effect, it would have to be off axis by 30°. Prevention of IOL rotation includes complete removal of Ophthalmic Viscosurgical Devices (OVDs), especially posterior to the IOL.

Most patients do extremely well following this surgical technique. The technical surgical learning curve for the surgeon is minimal for an outcome that is reliably predictable. Toric IOLs, exclusively or in conjunction with astigmatic keratotomy and/or strategic cataract incision placement, can result in excellent management of astigmatism.

### **9.6 Notification of deaths**

Any study death in relation to the cataract surgery should be reported by the corresponding surgeon and CI, following the *Care of Deceased Patient Policy* of the UHP. The study sponsor must also be notified as per the reporting of SAEs, SADEs and USADEs in 9.3.

### **9.7 The type and duration of the follow-up of participants after adverse reactions.**

All adverse events must be followed-up until resolution or death of the participant. Any events continuing at the end of the study will be followed up by the participants' GP and/or the routine clinical care team until discharge.

### **9.8 Reporting urgent safety measures**

Vision and balance changes after bilateral implantation of Toric IOLs  
IRAS ID: 286913

The investigator and sponsor have the authority to deviate from the protocol if doing so relates to the immediate safety of a participant, where continuing to follow protocol would put that participant at risk. This is classed as an urgent safety measure and must be reported to REC immediately and in any event within three days, in the form of a substantial amendment, that such measures have been taken and the reasons why.

## **10. STATISTICS AND DATA ANALYSIS**

### **10.1 Sample size calculation**

Sample size test calculation was carried out with the G\*Power 3.1 program (Faul *et al.*, 2007) for comparison of the main outcome measure of dynamic balance (between IOL design) using mixed ANOVA (repeated measures, between factor being the type of IOL).

Based on of the dynamic balance measurement (JERK score) in a previous study (Mancini *et al.*, 2011) an estimated medium effect size (0.25) will be used. With a power of 85% and level of significance ( $p$ ) set at 0.05 and effect size of 0.25, 55 participants will be required in each group (Monofocal vs Toric IOL). Accounting for a 20% drop out rate, 70 participants will therefore be recruited in each group (A total of 140 participants).

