#### **Sample size calculation:**

Sample size test calculation was carried out with the G\*Power 3.1 program (Faul *et al.*, 2007) for comparison of the main outcome measure of dynamic balance (between IOL design) using mixed ANOVA (repeated measures, between factor being the type of IOL).

Based on of the result of dynamic balance measurement in a previous study (Mancini *et al.*, 2011), an estimated medium effect size (0.25) will be used. With a power of 85% and level of significance ( $p$ ) set at 0.05 and effect size of 0.25, 55 participants will be required in each group (Standard non-Toric vs Toric IOLs). Assuming a 20% drop out rate, to secure 55 participants in each group, 70 participants will therefore be recruited in each group. For two groups of participants (Toric versus non-Toric), a total of 140 participants will be recruited.

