### 3.6 Table of endpoints/outcomes

Objectives	Outcome Measures	Timepoint(s) of evaluation of this outcome measure (if applicable)

Primary Objective To compare dynamic stability in cataract patients with Toric versus non-Toric IOLs
	
Dynamic stability: - movement of centre of mass and head tilting using wireless motion sensors.
	
Three timepoints:
 
 
1. pre-operation study visit and
 
2. post-operation study visit (3-6 months after first eye surgery).
 
3. post-operation study visit (3-6 months after second eye surgery).
 

Second Objectives To compare eye tracking characteristics, visual functions, risk of falls and quality of life in cataract patients with Toric versus non-Toric IOLs
	
Eye tracking characteristics: -area of interest by gaze pattern -Gaze duration on area of interest
 
Vision function include visual acuity, IOL rotation by degrees of rotation from intended position and degree rotation from the steepest meridian using special optometry equipment to look at the front of the eye (digital slit lamp and Pentacam)
 
Risk of fall will be measured by fear of falling and fall efficacy scale questionnaires. Vision related quality of life will be measured by CAT-PROM5 questionnaire.
	
Three timepoints:
 
 
1. pre-operation study visit and
 
2. post-operation study visit of first eye at 3-6 months after the surgery
 
3. post-operation study visit of second eye at 3-6 months after the surgery
 

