## 4. TRIAL DESIGN

The study is a randomized controlled trial comparing the change of dynamic stability, gaze characteristics, visual function, and quality of life measurements between Toric and non-Toric intraocular lens (IOL) groups.

Vision and balance changes after bilateral implantation of Toric IOLs  
IRAS ID: 286913

The study is a double masked, parallel group design. 140 cataract patients with astigmatism  $>1.0D$  at the Royal Eye Infirmary (REI) of Derriford Hospital will be recruited and randomly assigned to either receive Toric IOLs or non-Toric IOLs for bilateral lens replacement surgery. The randomization will be conducted by the CI who is not involved in the surgical intervention nor the outcome measure assessments. The participants will not know which types of IOLs they are receiving and the study coordinator who assesses the outcome measures will be masked to the types of IOLs given to the participants. Study visits will be carried out before surgery, 3-6 months after first and second eye surgery.

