### **10.3 Statistical analysis plan**

All data will be assessed for normality using a combination of assessing histogram plots and the Shapiro-Wilks Normality Test. Descriptive summary statistics for outcome measures relating to vision (acuity and refraction) will be recorded as mean +/- standard deviation.

Mixed ANOVA and post-hoc Bonferroni tests will be used to determine the statistical differences in the baseline characteristics and outcome measures between the Toric monofocal IOLs group and the non-Toric monofocal IOLs group. The between-subjects factor would be type of IOL lens and the within-subjects factor would be time (pre-surgery vs post-surgery). Level of significance will be set at 0.05.

Vision and balance changes after bilateral implantation of Toric IOLs  
IRAS ID: 286913

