### 10.3.2 Primary outcome analysis- Dynamic stability in three functional activities

The following outcomes will be collected at three time points: before surgery, 3 to 6 months after first and second eye surgery.

Outcome measures	Data collected	Data type/ details	Quantitative Statistical Analysis
Dynamic stability during turning, obstacle crossing and stair walking	Accelerometers data (angular position and acceleration) of change in head tilting and centre of mass will be recorded  Performance of TU&G test	Interval  Centre of mass and head movement will be calculated using ProMove 3D (Inertia Technology, The Netherlands) and MATLAB.  The angular position, velocity and acceleration of the sensors will be tracked on each participant  Duration in seconds of TU&G test	The average reading of the 3 trials in each functional activity will be calculated.  Mixed ANOVA and post-hoc Bonferroni tests will be used to determine the differences between the Toric IOLs group and Monofocal IOLs group before surgery and 6 months after second eye surgery.

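### The 85% power appears to belong to a between-lens main effect that averages in the pre-surgery visit, while the trial's question is about change and no primary test is named

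*Combined protocol and SAP*

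**What the plan says.** The sample size text appears in Section 3.3 and again in Section 10.1. Both use G*Power with a mixed ANOVA. Section 10.1 describes a comparison of the "main outcome measure of dynamic balance (between IOL design) using mixed ANOVA (repeated measures, between factor being the type of IOL", and states that with "effect size of 0.25, 55 participants will be required in each group". Section 3.3 gives the same number: "55 participants will be required in each group (Standard non-Toric vs Toric IOLs". Power is 85% and the significance level 0.05. A 20% dropout allowance takes the total to 140. Neither section states how many repeated measurements were entered, what correlation between them was used, or which term of the ANOVA was powered.

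Section 4 describes the study as a "randomized controlled trial comparing the change of dynamic stability" and other measures between the lens groups.

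Section 10.3 makes lens type the between-subjects factor and says "the within-subjects factor would be time (pre-surgery vs post-surgery", which is two levels. Section 10.3.2 says "The following outcomes will be collected at three time points", and the table in Section 3.6 lists the third of these as the "post-operation study visit (3-6 months after second eye surgery". The analysis column of 10.3.2 then applies the mixed ANOVA and post-hoc Bonferroni tests to the "differences between the Toric IOLs group and Monofocal IOLs group before surgery and 6 months after second eye surgery". None of these sections uses the word interaction or names a primary contrast.

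**The concern.** A mixed ANOVA with lens and time as factors yields several results: a lens main effect, a time main effect, a lens-by-time interaction and by-visit group differences. They answer different questions. The lens main effect asks whether the groups differ on average over all visits, including the one before any lens is implanted. Randomised groups have no lens effect at that visit, so including it dilutes the effect of interest. The interaction asks whether the groups change differently, which is what Section 4 describes.

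If the sample size was computed for the main effect, the stated 85% has not been shown to apply to the question the trial asks. Because the deciding result is unnamed, one dataset would also give several candidate p-values with quite different power, and the choice among them could be made after the data are seen.

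**Working it through.** **Inputs from the documents.** f = 0.25, alpha = 0.05, power 85%, 55 per group (N = 110), two groups, 70 per group recruited (Sections 3.3 and 10.1). Lens is the between factor and time (pre, post) the within factor (Section 10.3).

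**Assumptions, not in the documents.** The number of measurements m and the correlation r between visits are unstated; r = 0.5 is used, with a range of 0.3 to 0.7. For two groups f = 0.25 corresponds to d = 2f = 0.5, read here as a 0.5 SD difference after surgery and none before. SDs are taken as equal across visits and groups, and tests as two-sided.

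**Step 1: reproduce the plan's figure.** For a between factor, λ = N·m·f²/(1 + (m − 1)r), with 1 and N − 2 degrees of freedom.

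- m = 2, r = 0.5: 110 × 2 × 0.0625/1.5 = 9.17, power 85.1%.
- m = 3, r = 0.625: 110 × 3 × 0.0625/2.25 = 9.17, power 85.1%.
- m = 3, r = 0.5 needs only N = 98.
- m = 1 (a single visit): λ = 6.875, power 73.8%; 85% needs N = 146.

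For the interaction under G*Power's default effect-size convention, λ = N·m·f²/(1 − r). At r = 0.5 this needs N = 38 (m = 2) or 32 (m = 3). Even at r = 0 it needs only 74 or 60, and N falls as r rises, so it does not give 110. The between-lens main effect is therefore the likely source.

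**Step 2: power of that main effect for a post-surgery difference.** The two-visit average differs by (0 + 0.5)/2 = 0.25 SD. The SD of the average is √((1 + r)/2) = 0.866 at r = 0.5, so the standardised effect is 0.289. The noncentrality is 0.289 × √(55/2) = 1.51 and power is 32%. The main effect keeps 85% only if the average difference is 0.5 SD, for example 0.5 SD already present before surgery, or 1.0 SD after it.

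**Step 3: the other results available in the planned two-level ANOVA.**

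- Interaction, equivalent to comparing change scores: 0.5/√(2(1 − r)) = 0.5 at r = 0.5; noncentrality 2.62; power 74%.
- Visit 3 difference alone: 0.5 SD whatever r is; power 74%, or 64% at alpha 0.025 (Bonferroni over two visits).

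**Step 4: visit 3 adjusted for visit 1 (ANCOVA).** 0.5/√(1 − r²) = 0.577 at r = 0.5; noncentrality 3.03 on 107 degrees of freedom; power 85%. Its variance relative to the change score is (1 − r²)/(2(1 − r)) = (1 + r)/2, that is 0.65, 0.75 and 0.85 at r = 0.3, 0.5 and 0.7.

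| Power at r = 0.3 / 0.5 / 0.7 | 55 per group | 70 per group |
|---|---|---|
| Main effect, pre and post | 36 / 32 / 29% | 45 / 40 / 36% |
| Interaction, pre and post | 59 / 74 / 92% | 70 / 84 / 97% |
| Visit 3 difference, unadjusted | 74% at any r | 84% at any r |
| ANCOVA (not in the plan) | 78 / 85 / 95% | 87 / 92 / 98% |

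At 55 per group the interaction reaches 85% at r of about 0.62. Simulation with 20,000 runs per case, at 55 per group, agreed with the main effect, interaction and ANCOVA figures to within one percentage point.

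**The case against.** **Nothing is miscalculated.** This stands. The 55 per group reproduces, and 55/0.8 = 68.75 makes 70 a fair allowance for 20% dropout. A reader might infer an arithmetic error; the documents do not support that.

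**The powered term is inferred.** This also stands. Two unstated inputs were solved for. Under a different effect-size convention (the SPSS-type option) with three visits and a sphericity correction, an interaction comes close to 110: N = 108 at ε = 0.80 and 112 at ε = 0.75. That takes two non-default choices, and the wording of 10.1 points to the between factor, so the main effect is likelier but not established.

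**The 32% rests on an added reading of f.** Correct. Section 10.1 does not say the effect is absent before surgery and 0.5 SD after it. If f = 0.25 describes the averaged main effect itself, 85% is right as stated. But that would need a group difference before surgery, which randomisation gives no reason to expect, or a post-surgery difference of 1.0 SD.

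**Read together, the sections point to the pre-to-post interaction.** Section 4 speaks of change, 10.3 gives two time levels, and 10.3.2 picks the first and last visits. This is a reasonable reading, and on it power may be adequate. It remains the reader's construction: no section says so, and the sample size text points elsewhere.

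**A reader might also quote 85% as the upper end for the planned tests.** At r = 0.5 that figure belongs to ANCOVA, or to a contrast of the mean post-surgery value with baseline. The plan names neither.

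**Conclusion.** The point holds as a mismatch between the powered test and the trial's question, together with an unnamed primary test. That no primary test is named follows from the text alone. That the powered term is the between-lens main effect is an inference from the wording of 10.1 and the match at N = 110.

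The size of the problem depends on the assumed 0 SD before and 0.5 SD after surgery, and on r. At 55 per group and r = 0.5, none of the main effect, the interaction or the visit 3 difference reaches 85%. Over r = 0.3 to 0.7 the main effect stays low, but the interaction ranges so widely that it is tempting, and unsupported, to call the trial underpowered. With a high enough r, or with nearly everyone retained (Section 13.3 reports few dropouts in the team's earlier lens trials), the interaction has about the intended power.

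**What to change.** In Sections 10.3 and 10.3.2, name one primary test: the visit 3 value compared between lenses with the visit 1 value as covariate, by ANCOVA or the equivalent mixed-model contrast. Report the adjusted mean difference with its 95% confidence interval. Naming the visit 1 to visit 3 change as primary would also remove the mismatch, but it is less precise at any r below 1.

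In Sections 3.3 and 10.1, restate the power for that test and label its inputs as assumptions. For example: 55 per group gives 85% power for a 0.5 SD difference at visit 3 if the correlation between visits 1 and 3 is 0.5 (78% if 0.3, 95% if 0.7). If the team has a sourced correlation or SD-scale difference, use it instead.

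The cost is wording in four sections, with no extra participants, visits or data; the target stays at 140. The small downside is that the stated power becomes openly conditional on r. The restated power also depends on choosing a single primary variable from the several sensor measures and tasks in Sections 3.4 and 10.3.2, which is a separate point.

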### **10.2 Planned recruitment rate**

140 participants will be recruited over three-year period (minimal sample size of 110 plus 20% drop out rate estimation)

According to latest data from the National Ophthalmology audit database by the Royal College of Ophthalmologists, the REI of UHP performed 2525 cataract between 1st of September 2018 to 31st August 2019. The PI who performed cataract surgery at the REI reported around 3000 cataracts surgery were performed last year and the number is estimated to be similar this year. Due to COVID, there were longer waiting list and the waiting time between first and second cataract surgery at UHP has increased to about 4 months.

Approximately 40% patients undergo cataract surgery on both eyes (Jaycock, 2009 #281) (Day, 2015 #282). Among patients eligible for cataract surgery in NHS, 42% were reported to have mild to moderate astigmatism ( $>1.0$  D) (Day, 2019 #283). Therefore, it is estimated about 500 patients at REI annually will meet the inclusion criteria (needing cataract surgery in both eye with mild-moderate astigmatism) and our target for 140 participants out of the potential 1500 patients over three year

Vision and balance changes after bilateral implantation of Toric IOLs  
IRAS ID: 286913

should be a feasible number (10% of potential eligible patients), especially with the increasing number of cataract surgeries done every year.

### **10.3 Statistical analysis plan**

All data will be assessed for normality using a combination of assessing histogram plots and the Shapiro-Wilks Normality Test. Descriptive summary statistics for outcome measures relating to vision (acuity and refraction) will be recorded as mean +/- standard deviation.

Mixed ANOVA and post-hoc Bonferroni tests will be used to determine the statistical differences in the baseline characteristics and outcome measures between the Toric monofocal IOLs group and the non-Toric monofocal IOLs group. The between-subjects factor would be type of IOL lens and the within-subjects factor would be time (pre-surgery vs post-surgery). Level of significance will be set at 0.05.

Vision and balance changes after bilateral implantation of Toric IOLs  
IRAS ID: 286913

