### **7.6 Baseline data**

At each study visit based at the UoP, the participant's full name, DOB, address and contact details will be checked for identification purposes. These details will remain separate from the study data which will be identified using the unique study number allocated to the participants.

The outcome measures will include the following:

- General demographic information such as age, gender, ethnicity, relevant medical history, cataract diagnosis and vision assessment results. This will last about 10 minutes.
- Dynamic stability assessment lasts about 30 minutes. Three motion sensors will be put on the participants' body (neck, lower back and upper leg) and they will be asked to wear a special eye tracking glass (figure 1). After that, the participants will be asked to perform a Timed Up and Go (TUG) test which involves getting up from a chair, walking 3m-distance and return to sit back on the chair. They will also be asked to walk over obstacles on level ground and the last mobility task is walking up and down a standardized staircase. Movement outcomes will be measured using three-dimensional motion analysis

Vision and balance changes after bilateral implantation of Toric IOLs  
IRAS ID: 286913

(ProMove 3D, Inertia Technology, The Netherlands) and eye tracking data will be collected *via* Tobii-pro glasses 2 (Tobii AB, Sweden) (figure 2 and 3). Three trials will be taken to estimate the average and the best recorded time will be taken for the TUG test. As all the participants are active community dwelling elderly without mobility problem, the dynamic stability tasks are no more demanding than their usual daily activities. The PPI also include discussion about the demand of the assessment and all participants agreed the dynamic stability tests only required low level mobility and no concerns were raised.

- Some qualitative data will be collected *via* self-administered questionnaires which takes about 15 minutes. Risk of fall will be assessed with the short Fall Efficacy Scale (FES-short) and Fear of Falling questionnaire. Vision specific quality of life will be assessed with CAT-PROM 5 questionnaire.

- Standard visual function assessment will also be carried out to assess visual acuity and degree of astigmatism and this takes about 20 minutes.

A paper CRF has been prepared for this study to collect data directly relevant to the objectives and outcomes measures detailed in the protocol.

[figure not shown]
[figure not shown]

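### Section 10.3 plans significance tests between the arms before surgery and leaves the Bonferroni family undefined, while the trial is sized on a main effect that averages in the pre-surgery visit

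*Combined protocol and SAP*

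**What the plan says.** Section 10.3 (Statistical analysis plan) states that "Mixed ANOVA and post-hoc Bonferroni tests will be used to determine the statistical differences in the baseline characteristics and outcome measures" between the toric and non-toric groups. Lens type is the between-subjects factor, and time is the within-subjects factor with two levels, before and after surgery. "Level of significance will be set at 0.05".

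Section 10.3.2 applies the same methods to the primary outcome, to determine "the differences between the Toric IOLs group and Monofocal IOLs group before surgery and 6 months after second eye surgery". Section 10.3.3 repeats this for the secondary outcomes.

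Section 7.6 describes the baseline information as "General demographic information such as age, gender, ethnicity, relevant medical history, cataract diagnosis and vision assessment results". In the Appendix 2 schedule, demographics are ticked at study visit 1 only.

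Section 10.1 sizes the trial for a mixed ANOVA with lens type as the between factor: "an estimated medium effect size (0.25) will be used". "With a power of 85% and level of significance" 0.05, it arrives at 55 participants per group.

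No section says how many comparisons the Bonferroni correction covers, whether the pre-surgery comparison is one of them, or which term or contrast decides the primary result.

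**The concern.** Three things go wrong together.

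- **The pre-surgery tests have no treatment content.** No lens has been implanted at visit 1, so an arm difference there cannot be a lens effect. A small p-value invites unplanned adjustment or reinterpretation. A large one gives false reassurance.
- **The method does not fit the data.** Age, gender, ethnicity and diagnosis have no before-and-after pair to feed a time factor, and several are categorical. Visual acuity is repeated, so there the model can be fitted, but the pre-surgery comparison is still uninformative.
- **The comparison that matters is not isolated.** The informative quantity is the arm difference after second-eye surgery. The plan places it beside a pre-surgery contrast in a correction of unknown extent. The main effect on which the trial is sized dilutes it by averaging in the visit at which no effect can exist.

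At stake is whether the stated 85% power applies to the question the trial asks.

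**Working it through.** **Inputs.** From section 10.1: f = 0.25 (d = 2f = 0.5 for two equal groups), alpha 0.05, power 85%, 55 per group. From section 10.3: two levels of time. Assumed because not stated: two-sided tests, and correlation r between visits, taken as 0.5 with 0.3 and 0.7 as alternatives.

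**1. The plan's own figure.** For the between-groups effect in a repeated-measures ANOVA with m measurements, the noncentrality is λ = N f² m / (1 + (m − 1) r), with 1 and N − 2 degrees of freedom. With N = 110, m = 2 and r = 0.5:

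λ = 110 × 0.0625 × 2 / 1.5 = 9.17, which gives power 85.1%.

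So 55 per group reproduces. Other settings do not: m = 3 needs N = 98, and the lens-by-time interaction needs N = 38 (m = 2) or 32 (m = 3), all at r = 0.5. The trial was therefore evidently sized on the lens main effect, as section 10.1 indicates.

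**2. What that main effect detects.** The formula assumes that the 0.5 SD difference exists at both visits. If the arms are equal before surgery and differ by 0.5 SD after, the averaged difference is (0 + 0.5)/2 = 0.25 SD. The SD of a two-visit mean is √((1 + r)/2).

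| r | effective d | noncentrality, d × √(55/2) | power at 0.05 |
|---|---|---|---|
| 0.3 | 0.25/√0.65 = 0.310 | 1.63 | 36% |
| 0.5 | 0.25/√0.75 = 0.289 | 1.51 | 32% |
| 0.7 | 0.25/√0.85 = 0.271 | 1.42 | 29% |

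These figures use the two time levels given in section 10.3. They would change if all three visits entered the model.

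**3. The post-surgery contrast, with and without Bonferroni.** Two-sample comparison, 55 per arm. Unadjusted: d = 0.5, noncentrality 0.5 × √27.5 = 2.62. Adjusted for the pre-surgery value at r = 0.5: d = 0.5/√(1 − 0.25) = 0.577, noncentrality 3.03.

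| Contrasts counted | alpha | adjusted | unadjusted |
|---|---|---|---|
| 1 | 0.05 | 85.1% | 73.8% |
| 2 (before and after) | 0.025 | 77.4% | 63.7% |
| Loss | | 7.7 points | 10.2 points |

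With baseline adjustment, the same loss is 9.5 points at r = 0.3 (77.8% to 68.3%) and 3.6 points at r = 0.7 (95.3% to 91.7%).

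**4. Baseline characteristics.** The plan does not say how many will be tested. For illustration, with 10 or 20 independent tests and no real imbalance, the chance of at least one p < 0.05 is 1 − 0.95^10 = 40% or 1 − 0.95^20 = 64%. Both the count and the independence are assumptions, and related characteristics would change the figures.

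**The case against.** The strongest defence is that the loss in step 3 may not occur.

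- With two lens types there is only one arm comparison at any visit. If Bonferroni is applied within each visit, nothing is divided.
- Bonferroni is described as post hoc. If an omnibus mixed-ANOVA term at 0.05 decides the result, the correction does not touch it.
- Section 4 frames the trial as a comparison of change, so the before-and-after wording in 10.3.2 may simply name the two levels of time.

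All of this stands, so the 8 to 10 points are conditional. The omnibus route does not rescue the plan, however, if the deciding term is the main effect used for sizing (step 2). The lens-by-time interaction would isolate the effect, but it is equivalent to an unadjusted change-score comparison, with 74% power at r = 0.5, and the plan does not name it as decisive.

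Two stronger readings should be resisted.

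- A reader might infer a loss of up to 26 points. That needs a family of all six pairs of the four arm-by-time cells and an unadjusted test (74% to 48%). Section 10.3.2 names only between-arm differences. Even in a family of six, removing the pre-surgery contrast alone regains only 2.4 to 2.6 points.
- A reader might infer that any baseline difference must be chance. Under section 7.3 the PI has the allocation list when recruiting, and section 10.6 discards the data of participants withdrawn after missed visits. Imbalance in the analysed set could therefore reflect selection. A p-value would neither diagnose nor repair that.

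It is also fair to say that Bonferroni is the only multiplicity control named. Deleting it outright would leave several sensor measures over three activities uncorrected.

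**Conclusion.** The point holds in a limited form. The between-arm tests of baseline characteristics are explicit in section 10.3, are uninformative, and use a model that cannot be fitted to once-measured or categorical variables. The pre-surgery arm contrast in 10.3.2 and 10.3.3 adds nothing about treatment.

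The cost in power depends on a family that the plan does not define. It is about 8 to 10 points if the two named contrasts are counted (55 per arm, d = 0.5, two-sided, r = 0.5 for the adjusted figure). It is zero if the correction works within visits or an omnibus test decides.

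The firmer consequence is the mismatch in sizing. The main effect that reproduces 55 per group has about 32% power (29% to 36% for r from 0.7 to 0.3) for a 0.5 SD difference confined to the post-surgery visit. The documents do not show that this main effect will decide the trial, but they do not name another term or contrast that will.

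**What to change.** - **Section 10.3:** remove baseline characteristics from the testing sentence and report them descriptively by arm.
- **Sections 10.3.2 and 10.3.3:** drop the pre-surgery arm contrast. Make the between-arm difference at visit 3, adjusted for the pre-surgery value of the same outcome, the main contrast, reported with a 95% confidence interval.
- **Primary outcome:** name one dynamic-stability variable, in one activity, and test it at 0.05. If more than one variable or activity stays primary, keep a multiplicity correction across them and state the number of tests it covers.
- **Section 10.1, and its duplicate in 3.3:** restate power for this contrast. With 55 per arm and d = 0.5 it is 85% at r = 0.5, with 78% at r = 0.3 and 95% at r = 0.7 as the sensitivity range.

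The cost is a revision of the analysis text and the power statement, plus a decision by the team on the primary variable. It needs no new data, visits or participants.
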